All subjects will be receiving background prednisone therapy. Subjects with relapsing/refractory GCA will have active disease despite previous or concurrent steroid therapy. Prednisone treatment must be initiated at Screening for subjects not currently receiving steroid treatment. An increase in prednisone dose may be required for some subjects currently receiving therapy to stabilize their disease activity prior to randomization. Investigators may consider if higher doses of prednisone are warranted for subjects with visual manifestations. The prednisone dose for all subjects at Screening will be determined by the Investigator and may be adjusted in an open manner based on the subject's disease status per investigator discretion. At Baseline (Randomization), doses must be within 20-60 mg prednisone for the starting dose when the pre-specified prednisone taper is initiated. Subjects will remain on the prednisone dose they are receiving at Baseline for one week and then will decrease the dose at Week 1 as specified in the taper regimen. Subjects will follow the open-label prednisone taper regimen until they reach a 20 mg dose of prednisone, when the blinded prednisone taper regimen begins. Subjects receiving a 20 mg prednisone dose at Baseline will continue the 20 mg dose for one week and at Week 1 will initiate the blinded taper.

Following the Screening period, eligible subjects will be randomized to receive sirukumab (100 mg SC q2w or 50 mg SC q4w) or matching placebo. All subjects will receive prednisone during the 52-week double-blind treatment period according to a pre-specified taper regimen. Randomization will be stratified by baseline oral prednisone dose ( $<30$  mg/day or  $\geq 30$  mg/day). The number of relapsing/refractory subjects will be capped at approximately 50% to ensure that a sufficient number of subjects with new onset disease are recruited.

An Independent Data Monitoring Committee (IDMC) will be utilized to ensure external objective medical and/or statistical review of safety issues in order to protect the ethical and safety interests of subjects and to protect the scientific validity of the study. The composition, remit, and procedures of the committee are provided in the IDMC charter.

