1.1. Changes in the Planned Analysis due to Study Termination

This SAP reflects the analyses done given study termination, and are not aligned with planned analyses as per protocol.

Due to the sponsor's decision to terminate the study, data for the following endpoints/objectives are not available. Therefore, the following objectives will not be reported in this planned analysis:

- Pharmacokinetic objectives
- Immunogenicity objectives
- Pharmacodynamic objectives
- Pharmacogenetics objectives
- Vascular ultrasound objectives

Additionally:

- Available data for exploratory objectives / endpoints related to biomarkers will only be listed.
- No statistical analysis will be carried out for efficacy objectives / endpoints due to the limited number of subjects completing the study at week 52.
- However, [Section 2.1](#) and [Section 3.2](#) list respectively objectives and endpoints as specified in the protocol.
- Protocol endpoint "Median and cumulative prednisone dose over time" is modified to "Cumulative prednisone dose over time" as median prednisone dose will be provided as part of the summary statistics for cumulative prednisone dose.
- Protocol wording "GCA flare" is modified to "disease flare" for consistency across endpoints in this document.

Due to study termination on 10th October 2017, early withdrawal visits were completed for all subjects by 30th November 2017. All subjects are required to have a safety follow-up visit 16 weeks (+/- 1 week) after the early withdrawal visit. The study should be terminated for an individual subject after they have completed the 16-week safety follow-up visit, unless there is a need for additional post-study visits for continued evaluation of an ongoing adverse event. However, if an anti-IL6, any biologic or investigational agent is initiated, the subject will be withdrawn from the 16-week safety follow up.

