4.4. Analysis Visits

Data will be presented and analyzed according to the visit recorded in the database. For other efficacy and safety data that visit are entered, no visit windows will be defined as sites should have case report form (eCRF) instructions and training to ensure reasonable data entry. If a visit happens outside the protocol-defined window (Week X \pm 3 days), one of the following will be occur:

- If it is recorded as Week X visit, no visit re-mapping will be done (except for PRO endpoints and Part B visits) and the recorded visit will be used in all analysis.
- If it is recorded as unscheduled visit, it will be treated as unscheduled visit.

In general, only those assessments which are assigned to an analysis visit will be included in the summary tables and figures and will be presented by visit. Unscheduled visits will not be included in summary tables or figures, with the following exceptions: if the table or figure includes data values for all post-baseline assessments (worst/best/maximum/minimum post-baseline assessments), or for tables which report the values during a period of time, unscheduled visits will be included. All unscheduled visits will be included in the listings.

When reporting results or events that are reported on an ongoing basis, such as cumulative prednisone dose or flare at Week X: All results/events will be taken into account that occur inclusively between the day after the Week X-1 visit and the day of the Week X visit. The actual day of the Week X visit will always be taken into account as the day of visit X, even if the actual visit occurred outside of planned visit window.

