4.6.3. Cumulative Prednisone Dose over Time

4.6.3.1. Main Analysis

For the main analysis of cumulative prednisone dose over time (mentioned in [Section 8.2.1](#)), data from subjects who permanently discontinue SC IP prior to completing week 52 visit due to any reason and continue in the study will be used for the analysis. Cumulative prednisone dose will be set to missing once a subject withdraws from the study.

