Summary statistics of cumulative prednisone intake including both taper and rescue medication will be summarized by treatment group and visit as well as overall.

Further discussions regarding the statistical analysis of cumulative prednisone intake including both taper and rescue medication is presented in [Section 8.2.1](#).

Frequencies are free text variables and need to be converted to numerical values. The following free text frequencies will be derived as follows:

Text	Frequency used for conversion
1 OF THE 3 DAYS	1/3
2 OF THE 3 DAYS	2/3
BID	2
DAIL	1
DAILY FOR 2 WEEKS	1
DQ	1
EVERY OTHER DAY	1/2
EVERY 12 HOURS	2
EVERY 2 OF 3 DAYS	2/3
EVERY 2 OF THE 3 DAY	2/3
EVERY 2 OF THE 3DAYS	2/3
EVERY 3TH DAY	1/3
EVERY TWO DAYS	1/2
EVERYDAY	1
EVRY DAY	1
MANE	1
ONCE	1
ONCE DAY	1
ONCE A DAY	1
ONCE D AY	1
ONCE EVERY DAY	1
ONCE OVER A DAY	1
ONCE THE DAY	1
ONCE/DAY	1
ONVE A DAY	1
Q3D	1/3
Q8H	3
QD	1
QOD	1/2
TID	3

8. Efficacy Analysis

All efficacy analyses will be based on the ITT set defined in [Section 4.4.3](#), unless otherwise specified. Subjects will be analyzed according to the treatment groups that they were randomized to, regardless of the treatments they actually received.

Only summary statistics will be produced given study termination.

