8.2. Secondary Efficacy Endpoints

8.2.1. Cumulative Prednisone Dose (Study Drug and Corticosteroid Rescue Therapy) over Time

Cumulative prednisone is the cumulative prednisone dose from the taper (both open-label and blinded) as well as from the corticosteroid rescue therapies, as defined in [Section 3.3](#) and [Section 7.3](#). Cumulative dose at Week X will be derived as the sum of all the doses from baseline to Week X. If a subject withdraw from study between two scheduled visits, all prednisone doses recorded between his last scheduled visit and study withdrawal will be associated to the next scheduled visit. For example, if a subject withdraw between the Week 24 visit and the Week 28 visit, all doses recorded after the day of Week 24 will be associated to Week 28. For more details on imputation of missing data for the key secondary endpoint, please refer to [Section 4.6.3.1](#).

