8.2.1.1. Statistical Analysis

The cumulative prednisone dose will be summarized by treatment group and visit. Interquartile range (IQR) will also be displayed in summary statistics. The summary statistics will be generated for the total cumulative prednisone as well as for the study drug and the CS rescue therapy separately. Cumulative dose will be listed.

8.2.2. Proportion of Subjects in Sustained Remission over Time from Week 12 to Week 52

For each visit (referred to as Week X in the algorithm below) from Week 12 to Week 48, the definition of sustained remission is similar to Week 52:

1. Remission at Week 12

Remission is defined as having achieved the 2 following criteria:

- c. Clinical remission is defined as absence of clinical signs and symptoms of GCA
- And
- d. Normalization of ESR (<30mm/hr) and CRP (<1mg/dL).

A subject in clinical remission is a subject that does not have any signs and symptoms, which is also determined by a lack of flare for the subject. If a subject does have a flare, they will have one or more signs and symptoms, and therefore are not considered as being in clinical remission.

The following rule will be used to assess remission at Week 12:

“Has the patient flared since their last visit?” should be answered “No” at Week 12 visit on the Clinical Assessment of GCA eCRF page and ESR laboratory results value at Week 12 $< 30\text{mm/hr}$ and CRP laboratory results value at Week 12 $< 1\text{mg/dL}$.

AND

2. Absence of disease flare following remission at Week 12 through Week X

Flare is defined as recurrence of symptoms attributable to active GCA, with or without elevations in ESR and/or CRP.

The following rule will be used to assess absence of disease flare following remission at Week 12 through Week X:

“Has the patient flared since their last visit?” should be answered “No” at each scheduled and unscheduled visit from any visit after Week 12 up to Week X on the Clinical Assessment of GCA eCRF page.

AND

3. Completion of the assigned prednisone taper protocol (to Week X)

“Can the patient continue with the protocol defined taper” on the Clinical Assessment of GCA eCRF page should be answered “Yes” at all visits between Baseline and the visit before the Week X visit.

AND

4. No requirement for rescue therapy at any time through Week X

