If any concomitant corticosteroid medication when the unit is not in (Actuation, Application, Area under curve, Cubic centimeter, Cells, Cells per kilogram, Fingertip unit, Drops, Gum, Inhalation, Kilocalories, Minimum alveolar concentration, Mega becquerels (MBq), Millicurie, Nebule, Patch, Powder, Puff, Ring, Spray, suppository) or any of concomitant non-corticosteroid medication identified as “GCA related” with the question “Was drug administered as a rescue medication?” is ticked as “Yes” and if the first SC IP date \leq Concomitant medication start date \leq Week X visit date, then the subject will fail the criterion.

Please note that once a subject fails a criterion, he/she will also fail all future criteria from subsequent visits.

For more details on imputation of missing data for sustained remission endpoint, please refer to [Section 4.8.2.1](#).

If all of the 4 items are met and the subject did not discontinue SC IP before the Week X visit date, the subject will be considered in sustained remission at Week X. If 1 of the 4 items is not met or if the subject discontinued SC IP before the Week X visit, the subject will be considered as not in sustained remission at Week X.

Given study termination, only the subset of subjects who attended the Week X visit or who discontinued study treatment or withdrew from study prior to the 10th of October 2017 will be included in this analysis.

Number of subjects who flared and subjects who did not complete the prednisone blinded taper will also be summarized over time on the ITT Set.

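### SAP 8.2.1 and 4.6.3.1 disagree on a withdrawer's cumulative prednisone dose at the next scheduled visit; non-mg rescue records and the 12-month taper tables also need tidying (minor, descriptive analysis).

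*SAP*

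**What the plan says.** **Withdrawal.** SAP 8.2.1 defines the cumulative dose at Week X as everything taken from baseline to Week X, taper plus corticosteroid rescue. SAP 4.4 counts ongoing events and doses that "occur inclusively between the day after the Week X-1 visit and the day of the Week X visit". For a subject who leaves between visits, 8.2.1 adds that "all prednisone doses recorded between his last scheduled visit and study withdrawal will be associated to the next scheduled visit"; its example books an exit between Weeks 24 and 28 to Week 28. SAP 4.6.3.1 states: "Cumulative prednisone dose will be set to missing once a subject withdraws from the study". Section 8.2.1 refers the reader to 4.6.3.1 but gives no order of precedence.

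**Reporting.** SAP 8.2.1.1: "The cumulative prednisone dose will be summarized by treatment group and visit". SAP 7.3 also plans statistics for taper plus rescue that "will be summarized by treatment group and visit as well as overall". For remission by visit, SAP 8.2.2 includes "only the subset of subjects who attended the Week X visit or who discontinued study treatment or withdrew from study" before 10 October 2017. The dose sections carry no such restriction. SAP 4 (General Statistical Considerations) treats early withdrawal visits as scheduled visits.

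**Units.** SAP 7.3 first says that all corticosteroid dosages on the corticosteroid page will be converted to prednisone equivalents, then that only records in mg will be. The rescue rule in SAP 3.3 and 8.1 excludes a list of units that does not contain gram or microgram.

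**Taper tables.** Protocol Table 1 and SAP Table 3 both give the 12-month blinded taper. SAP 7.2.2.2 gives planned capsules for each blinded week. SAP 7.2.1 computes study-drug dose as days multiplied by the scheduled dose.

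**The concern.** In the SAP's own example the Week 28 visit falls after withdrawal. Section 8.2.1 puts a number in that cell and 4.6.3.1 leaves it empty, so two programmers following the SAP could produce different tables for what 8.2.1 calls the key secondary endpoint.

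Even if the two rules are harmonised (a value at the next visit, missing from then on), the number is dose to exit and not dose to Week X. It enters the same mean, median and interquartile range as full-interval values. Early termination makes this more than a rarity: subjects still on study had early withdrawal visits by 30 November 2017, and SAP 1.1 drops efficacy testing "due to the limited number of subjects completing the study at week 52".

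The other two points affect the same sum. A rescue record in grams would fail the remission criterion but have no defined dose, and the expected Arm E dose depends on which taper table is used.

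**Working it through.** **Inputs.** Weekly doses from Protocol Table 1 and SAP Table 3, one week per row. Baseline dose from Protocol 4.1: "doses must be within 20-60 mg prednisone for the starting dose when the pre-specified prednisone taper is initiated". Visits from Protocol Table 2: Weeks 2, 4, 8 and then every four weeks to Week 52.

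**Step 1: the plan's own figure.** The capsule table in SAP 7.2.2.2 has 45 blinded weeks. The 12-month column of SAP Table 3 also has 45, with four weeks at 4 mg, matching the four weeks (30-33) at four capsules. Protocol Table 1 has 46, with five weeks at 4 mg.

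**Step 2: largest shortfall for one leaver, taper only.** This is the full taper dose between two consecutive visits, approached when exit comes just after the earlier visit.

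- 6-month, Week 8, 20 mg start: 7 × (10+9+8+7) = 238 mg.
- 6-month, Week 8, 60 mg start: 7 × (30+25+20+15) = 630 mg.
- 6-month, Week 28: 0 mg from a 20 mg start; 7 × (1+1) = 14 mg from 60 mg.
- 12-month (SAP), Week 28: 7 × (6+6+5+5) = 154 mg from 20 mg; 7 × (7+7+7+7) = 196 mg from 60 mg.

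Ranges over baseline doses of 20-60 mg:

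| Row | 3-month | 6-month | 12-month (SAP) |
|---|---|---|---|
| Week 4 | 105-525 | 175-525 | 224-525 |
| Week 8 | 28-630 | 238-630 | 336-651 |
| Week 12 | 0-133 | 154-308 | 266-420 |
| Week 16 | 0 | 98-189 | 238-280 |
| Week 28 | 0 | 0-14 | 154-196 |
| Week 52 | 0 | 0 | 0-28 |

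**Step 3: the SAP's example, exit one day after Week 24, taper only.** For the 12-month taper from 60 mg, 8.2.1 gives 3,122 + 7 = 3,129 mg, 4.6.3.1 gives missing, and the completed interval gives 3,318 mg: 189 mg short. From 20 mg the values are 1,728 and 1,876 mg: 148 mg short. For the 6-month taper from 60 mg they are 2,619 and 2,632 mg: 13 mg short. The 3-month taper shows no difference.

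**Step 4: rescue.** The documents give no rescue dose. Each assumed 10 mg/day still being taken adds up to 28 × 10 = 280 mg to the shortfall in a four-week interval.

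**Step 5: the 12-month tables.**

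- From 60 mg, open-label weeks: 7 × (60+50+40+35+30+25+20) = 1,820 mg.
- SAP total: 1,820 + 2,086 = 3,906 mg over 52 weeks.
- Protocol total: 1,820 + 2,114 = 3,934 mg over 53 weeks. The last 7 mg falls after Week 52, leaving 3,927 mg.
- Difference by Week 52 from 60 mg: 3,927 - 3,906 = 21 mg.
- Starts of 20-50 mg finish within 52 weeks on either table, so the difference is the whole extra week, 7 × 4 = 28 mg (from 20 mg: 2,254 against 2,226 mg).

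**Step 6: units.** No arithmetic follows from the documents. They show no gram or microgram record and assign no value to one.

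**The case against.** The two withdrawal rules can be reconciled: 8.2.1 is specific to the interval of exit, 4.6.3.1 is general, and the natural combination affects one cell per leaver. That reading is reasonable, but the SAP does not state it, and it leaves the mismatch with the row definition.

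The booked dose is also drug actually taken. Setting it to missing discards real exposure from the row and leaves attenders only. This stands, which is why dose to withdrawal should still be reported elsewhere.

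Four stronger readings are tempting and are not supported.

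- *The by-visit means are biased low, or the A-versus-D comparison is.* A leaver's value is low against that subject's own completed interval. Leavers may differ from stayers in starting dose and rescue use, so the net direction for a row is unknown. Arms A and D share the 6-month taper, so their taper component has no truncation at Week 52.
- *Every leaver contributes a truncated value.* Not once the taper has ended and no rescue is being taken: from Week 16 in the 3-month arm, and after Week 28 on the 6-month taper.
- *Everyone stopped by termination enters the next row.* The dose rules do not prevent it, but SAP 4 counts early withdrawal visits as scheduled, so the row these subjects belong in is unclear.
- *Gram and microgram records count as 0 mg.* SAP 7.3 says only that such records are not converted; a zero contribution is an inference.

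On the taper tables, the difference is small and the SAP agrees with itself. An extraction error in the protocol column cannot be excluded, but the passages still need to be compared.

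**Conclusion.** The point holds as a minor correction. SAP 8.2.1 and 4.6.3.1 give different answers for one cell per between-visit leaver, and the 8.2.1 value does not match its row definition while dosing is still due. The per-subject size is largest early in the taper and small or nil late in the 3- and 6-month regimens; rescue would add to it by an amount the documents do not allow one to state. The effect on any row cannot be given, because the number of leavers, their starting doses and their rescue use are not reported. The bounds assume one taper row per week and adherence to the schedule.

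The handling of non-mg rescue records is undefined, and whether any exist is unknown. The 12-month tables differ by one week at 4 mg, which changes the expected Arm E dose by 21 or 28 mg by Week 52 (about 0.5% from a 60 mg start: 21/3,906). Only summary statistics are planned, so no test, power or error rate is affected.

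**What to change.** 1. In SAP 8.2.1, apply 4.6.3.1: set Week X to missing when withdrawal precedes the Week X visit, and print the number withdrawn beside each row.
2. Report dose to withdrawal in the early-withdrawal row, or in the overall summary already planned in 7.3, with overall defined as baseline to withdrawal or Week 52. State which row applies to subjects who leave because of termination.
3. In SAP 7.3, convert gram and microgram records to mg before applying the factors, and state how any other unit allowed by the rescue rule is handled.
4. Reconcile the 12-month columns of Protocol Table 1, SAP Table 3 and the capsule table. No view is taken here on which is right.

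The cost is SAP wording and some reprogramming on data already collected. The drawback is fewer non-missing values at later visits: those rows then describe attenders only, so the number withdrawn must appear with them.

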8.2.1.1. Statistical Analysis

The cumulative prednisone dose will be summarized by treatment group and visit. Interquartile range (IQR) will also be displayed in summary statistics. The summary statistics will be generated for the total cumulative prednisone as well as for the study drug and the CS rescue therapy separately. Cumulative dose will be listed.

8.2.2. Proportion of Subjects in Sustained Remission over Time from Week 12 to Week 52

For each visit (referred to as Week X in the algorithm below) from Week 12 to Week 48, the definition of sustained remission is similar to Week 52:

1. Remission at Week 12

Remission is defined as having achieved the 2 following criteria:

- c. Clinical remission is defined as absence of clinical signs and symptoms of GCA
- And
- d. Normalization of ESR (<30mm/hr) and CRP (<1mg/dL).

A subject in clinical remission is a subject that does not have any signs and symptoms, which is also determined by a lack of flare for the subject. If a subject does have a flare, they will have one or more signs and symptoms, and therefore are not considered as being in clinical remission.

The following rule will be used to assess remission at Week 12:

“Has the patient flared since their last visit?” should be answered “No” at Week 12 visit on the Clinical Assessment of GCA eCRF page and ESR laboratory results value at Week 12 $< 30\text{mm/hr}$ and CRP laboratory results value at Week 12 $< 1\text{mg/dL}$.

AND

2. Absence of disease flare following remission at Week 12 through Week X

Flare is defined as recurrence of symptoms attributable to active GCA, with or without elevations in ESR and/or CRP.

The following rule will be used to assess absence of disease flare following remission at Week 12 through Week X:

“Has the patient flared since their last visit?” should be answered “No” at each scheduled and unscheduled visit from any visit after Week 12 up to Week X on the Clinical Assessment of GCA eCRF page.

AND

3. Completion of the assigned prednisone taper protocol (to Week X)

“Can the patient continue with the protocol defined taper” on the Clinical Assessment of GCA eCRF page should be answered “Yes” at all visits between Baseline and the visit before the Week X visit.

AND

4. No requirement for rescue therapy at any time through Week X

If any concomitant corticosteroid medication when the unit is not in (Actuation, Application, Area under curve, Cubic centimeter, Cells, Cells per kilogram, Fingertip unit, Drops, Gum, Inhalation, Kilocalories, Minimum alveolar concentration, Mega becquerels (MBq), Millicurie, Nebule, Patch, Powder, Puff, Ring, Spray, suppository) or any of concomitant non-corticosteroid medication identified as “GCA related” with the question “Was drug administered as a rescue medication?” is ticked as “Yes” and if the first SC IP date \leq Concomitant medication start date \leq Week X visit date, then the subject will fail the criterion.

Please note that once a subject fails a criterion, he/she will also fail all future criteria from subsequent visits.

For more details on imputation of missing data for sustained remission endpoint, please refer to [Section 4.8.2.1](#).

If all of the 4 items are met and the subject did not discontinue SC IP before the Week X visit date, the subject will be considered in sustained remission at Week X. If 1 of the 4 items is not met or if the subject discontinued SC IP before the Week X visit, the subject will be considered as not in sustained remission at Week X.

Given study termination, only the subset of subjects who attended the Week X visit or who discontinued study treatment or withdrew from study prior to the 10th of October 2017 will be included in this analysis.

Number of subjects who flared and subjects who did not complete the prednisone blinded taper will also be summarized over time on the ITT Set.

